## 8.2 Key Secondary Outcomes

- Mortality is a key secondary outcome; analyses are described in section 7.
- To supplement the separate analyses of time to sustained recovery and time to death, the two endpoints will be analyzed jointly using the “win ratio” method for the composite outcome of time to recovery or death. The win ratio will be calculated using the matched pairs method described in Pocock (2012). Pairs will be formed by ranking the participants in each treatment group according to a risk score, described in section 13.2, and pairing the participants in groups A (here referring to the investigational drug) and B (referring to control) with equal ranks. Details are given below.
  - If both treatment groups have the same number of observations, the win ratio is calculated as follows:
 

**Step 1:** Calculate the risk score for all participants, and order participants by the risk score in each treatment group. If needed, break ties at random. Each participant forms a “matched pair” with the participant of equal rank order in the other treatment group.

**Step 2:** For each pair, determine whether the participant in group A wins, loses, or neither:

    - a. *Compare pairs for time to death, for all pairs where one or both participants died.* If the participant in group A died, wins and losses are computed as follows:
      - If the matched participant in group B has longer follow-up, then A loses and B wins.
      - If the matched participant in group B has shorter follow-up and is alive at the censoring date, then neither group wins.

Repeat for pairs where the participant in group B died.

b. *Compare remaining pairs for time to sustained recovery.*

- If A achieved sustained recovery, and time to sustained recovery is longer for B, then A wins and B loses; vice versa for B.
- If A achieved sustained recovery, and B was censored without reaching sustained recovery before A reached sustained recovery, then neither group wins; vice versa for B.
- Otherwise, neither group wins.

**Step 3:** Calculate the win ratio as the number of wins in group A divided by the total number of pairs with a win or a loss in group A. Calculate the 95% CI for the win ratio and p-value as described in Pocock (2012).

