- If one treatment group has more participants than the other, select  $|n_A - n_B|$  participants at random from the larger group and delete. Calculate the win ratio, 95% CI and p-value for the resulting matched pairs. Repeat the random selection of observations to delete 501 times; identify the matched pairs data set that corresponds to the median win ratio; the final values of the win ratio, 95% CI and p-value are those calculated from this data set.
- If both treatment groups have the same number of observations, but some ranked risk scores are tied within a treatment group, a similar process may be used to repeat the random breaking of ties, with the final win ratio chosen as the median over repeated random tie breaks.

With this approach, time to death is first used to determine the winning group (i.e., longer time to death), then time to sustained recovery is used to determine the winning group (i.e., shorter time to recovery): in this manner, the win ratio combines these conflicting outcomes into a composite while recognizing the importance of mortality.

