### E-3 Power Estimation Prior to Unblinding

On December 28, 2021, prior to unblinding any treatment comparisons for the trial of AZD7442, power was re-assessed based on updated pooled (AZD7442 and placebo groups combined) primary endpoint results. Pooled primary outcome data on December 28, 2021 are given in the table below.

**Table E-1.** Recovery status of participants in the AZD7442 trial as of December 28, 2021

	1455 Participants Randomized				
	1417 Infused and 38 not infused (35 withdrew consent)				
	nAb negative	nAb positive	Specimen not yet analyzed	Specimen not available	TOTAL
Recovery status through Day 90	N=616	N=657	N=107	N=37	N=1417
Withdrew prior to recovery	2	4	0	0	6
Day 90 window closed and recovery status unknown	17	5	0	1	23
Day 90 window not yet closed* and recovery status unknown	0	1	3	0	4
Achieved sustained recovery	508	586	76	25	1195
Home < 14 days	7	5	0	0	12
Discharged from hospital, but not home	9	3	0	2	14
Hospitalized	12	10	2	1	25
Died before recovery	61	43	26	8	138

\* The Day 90 window extends to Day 100.

The mITT study population included 1417 participants. At this time, most of the 90-day follow-up was completed. The last patient was randomized on September 30, 2021 and the visit window for the Day 90 visit extends to 100 days (January 8, 2022).

Overall, the number of primary events was 1,195, 33 events less than the target of 1,228. As the table below indicates, this does not have a material effect on power.

**Table E-2.** Power estimates in the full study population: Recovery rate ratios (RRR) that can be detected with 80-90% power and 0.05 (2-sided) significance level, assuming 1195 sustained recovery events pooled across treatment groups

Power	RRR
0.90	1.206
0.85	1.189
0.80	1.176

**Table E-3** below summarizes power estimates for the subgroup of participants who were nAb-negative at study entry. This subgroup is currently 48% of those for whom the baseline nAb status was determined. We anticipate results for 107 additional patients in January 2022. The effect sizes (recovery rate ratio [RRR]) that can be detected with 90%, 85%, and 80% power for different estimates of the final number of primary events for the nAb-negative subgroup are summarized below; as of December 28, 2021, 508 participants in this subgroup had achieved sustained recovery, and 76 participants among those for whom the nAb status is not yet known.

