### Analysis Population

Treatment comparisons for efficacy and safety outcomes will be by modified intention-to-treat (mITT). The mITT analysis is restricted to participants who received a complete or partial infusion of MP0420/placebo; participants who did not receive any MP0420/placebo are excluded. The TICO platform protocol specifies ITT for the efficacy analyses “unless otherwise stated”, and mITT for safety analyses.

*Justification for changing the study population to mITT for efficacy analyses:* In the TICO trial of MP0420, 496 participants were randomized (ITT population). Of these, 485 were infused (complete or partial) with MP0420/placebo and 11 were not. Of the 11 participants not infused, 9 withdrew consent prior to infusion. Follow-up data after Day 0 was collected for the 2 participants not infused, but remained consented. Because the treatment assignment was blinded, the risk of bias due to restricting analyses to the mITT cohort is low. With this approach, the risk and benefits of MP0420 will be evaluated in the same population.

**Comment:** Investigators were unblinded to summaries of the infusion status of participants, pooled across treatment groups. These analyses were included in the open DSMB reports.

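### SAP section 8.2, Step 3 defines the win ratio as wins over decided pairs, which is a proportion with null 0.5, and states no null value

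*SAP*

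**What the plan says.** SAP section 8.2 lists a matched-pairs win ratio among the key secondary outcomes. Participants are ranked by risk score within each arm and paired by rank, with "groups A (here referring to the investigational drug) and B (referring to control) with equal ranks". Step 2 gives each pair one of three results for A: win, loss or neither. Death is compared first, then time to sustained recovery.

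Step 3 gives the estimator: "Calculate the win ratio as the number of wins in group A divided by the total number of pairs with a win or a loss", counting pairs from A's side. It then continues: "Calculate the 95% CI for the win ratio and p-value as described in" a cited methods paper.

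If the arms differ in size, participants are deleted at random from the larger arm, the calculation is repeated 501 times, and the analyst is to "identify the matched pairs data set that corresponds to the median win ratio". That step keeps the name win ratio and gives no other formula. No section states a null value for the statistic.

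The direction is implicit but clear. A is the investigational arm, and a win means longer survival or, failing that, earlier recovery, so larger values favour the agent.

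**The concern.** A quantity called a win ratio is naturally read as wins divided by losses, with 1 meaning no difference. Step 3 divides wins by wins plus losses. The name and the formula therefore describe two different scales, and the missing null value leaves the reader to guess which one applies.

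Two things are at stake for a key secondary result:

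- **Misreading.** Every value of the Step 3 statistic is at or below 1. A clear advantage for the agent, such as 0.60, would look like harm if read against 1. The SAP's nearby reading rule, in section 8.1, puts superiority at values above 1. It covers only the recovery rate ratio, but a reader may carry it over.
- **Estimate and interval on different scales.** The estimate is defined in the SAP, while the interval is handed to the cited paper. If that paper gives its interval for wins over losses, the two would not match. The paper is not available here, so this is a possibility and not a finding.

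**Working it through.** The SAP gives no numerical win ratio, null or power for this analysis, so there is no plan figure to reproduce. The check evaluates the Step 3 formula directly.

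**Inputs**

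- Formula W/(W+L), where W and L are the pairs A wins and loses (SAP 8.2, Step 3). Undecided pairs are outside the denominator (Step 2).
- Planned size of 500 per arm, so 500 pairs (SAP 1.4).
- AZD7442: "The mITT study population included 1417 participants" (SAP Appendix E-3), so at most 708 pairs.
- MP0420: "Of these, 485 were infused (complete or partial) with MP0420/placebo and 11 were not" (SAP Appendix G, Analysis Population), so at most 242 pairs.
- Assumed, with no source in the documents: 90% of pairs decided, and wins over losses near 1.25.
- Assumed interval, because the cited method is not available: Wald limits for the proportion, transformed to the ratio scale.

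**Formulas**

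- p = W/(W+L), SE = sqrt(p(1−p)/(W+L)), 95% CI = p ± 1.96 SE.
- W/L = p/(1−p), with the limits transformed in the same way.
- Test on the proportion scale: z = (W−L)/sqrt(W+L). Test on the log ratio scale: z = ln(W/L)/sqrt(1/W+1/L).

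**Null and range.** If W = L, then p = 0.5 and W/L = 1. If L = 0, then p = 1, its maximum, while W/L has no upper bound. A simulation with wins and losses equally likely and 400 decided pairs gave a median of 0.50 for Step 3 and 1.00 for W/L.

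**Range of effects, assuming 400 decided pairs**

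| Wins / losses | Step 3 | W/L |
|---|---|---|
| 160 / 240 | 0.40 | 0.67 |
| 200 / 200 | 0.50 | 1.00 |
| 220 / 180 | 0.55 | 1.22 |
| 240 / 160 | 0.60 | 1.50 |

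**Worked example, planned size.** 0.9 × 500 = 450 decided pairs, split 250/200.

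- p = 250/450 = 0.5556; SE = sqrt(0.5556 × 0.4444/450) = 0.0234; CI 0.510 to 0.601.
- W/L = 1.25; limits 0.5096/0.4904 = 1.04 and 0.6015/0.3985 = 1.51.
- Proportion scale: z = 50/sqrt(450) = 2.357, p-value 0.0184. Log ratio scale: z = 0.2231/0.0949 = 2.352, p-value 0.0187.

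**All three sizes**

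| Setting | Wins / losses | Step 3 (95% CI) | W/L (95% CI) | p-values (proportion, log ratio) |
|---|---|---|---|---|
| Planned, 500 pairs | 250 / 200 | 0.556 (0.510–0.601) | 1.25 (1.04–1.51) | 0.018, 0.019 |
| AZD7442, 708 pairs | 354 / 283 | 0.556 (0.517–0.594) | 1.25 (1.07–1.46) | 0.005, 0.005 |
| MP0420, 242 pairs | 121 / 97 | 0.555 (0.489–0.621) | 1.25 (0.96–1.64) | 0.104, 0.105 |

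**Median of the 501 repetitions.** p/(1−p) is strictly increasing and 501 is odd, so both scales select the same data set.

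**Conditional mismatch.** Only if the cited interval is on the W/L scale, a literal reading of Step 3 would at planned size put 0.556 beside 1.04 to 1.51. With 450 decided pairs, the estimate would lie below its own interval once A wins at least 97 pairs (93 with a log-scale interval), about a fifth of them.

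**The case against.** The strongest reply is that the SAP does not contradict itself. It defines its statistic explicitly, the formula can be computed, and the same quantity is carried through the median step. A reader of Step 3 can work out that equal wins and losses give 0.5. On this view the point is one of terminology. The consequences are also limited: the p-value, the pairing, the win rules and the selected data set do not depend on the scale, and wins over losses can be recovered as p/(1−p). The analysis is introduced as a supplement to the separate analyses of recovery and death, and it has no alpha allocation, power or stopping role. The illustrative counts are assumptions, and the three sample sizes repeat one algebraic identity. The mismatch between estimate and interval rests on a paper that cannot be seen here.

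Much of this stands. The test is not invalid, no trial decision hangs on the scale, the figures illustrate size and do not predict results, and the mismatch is unproven.

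It does not remove the core point. The name says ratio and the formula gives a proportion. Being able to deduce the null does not help a reader who sees only the reported label and value. The citation does not settle it either: Step 3 writes out its own estimator, and a programmer is entitled to follow it.

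**Conclusion.** The concern holds. Step 3 defines a win proportion, with null 0.5 and maximum 1, under the name win ratio, and the SAP states no null value. This follows from the text alone and needs neither the assumed counts nor the cited paper.

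The size is a change of scale in the reported estimate: about 0.556 in place of 1.25 if wins exceed losses by a quarter, or 0.60 in place of 1.50 if they exceed them by half. The damage is confined to the estimate, possibly its interval, and how both are read. The p-value is essentially unchanged under the normal approximations used, and the median data set is the same. It should be corrected before results are reported, because it affects a key secondary outcome, but it does not threaten the validity of the comparison.

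**What to change.** Choose one of two wordings for section 8.2.

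1. **Ratio.** *The win ratio is the number of pairs in which A wins divided by the number in which A loses. The null value is 1, and values above 1 favour the investigational agent.*
2. **Proportion.** Keep the Step 3 formula, rename it *win proportion* in Step 3 and in the paragraphs on unequal group sizes and tied scores, and state that the null value is 0.5 and that values above 0.5 favour the agent.

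In either case add: *The 95% CI is reported on the same scale as the estimate.* Keep the cited method for the interval. Under option 1, transform its limits by p/(1−p) only if that method gives them for the proportion. Under option 2, transform by r/(1+r) only if it gives them for wins over losses. Whoever makes the edit should check the cited paper for this.

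The cost is one or two sentences in the SAP and a small change to the estimate line in the analysis program. No new data or unblinded information is needed, and the pairing, the test and the 501 repetitions stay as they are.

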### 8.3 Other Secondary Outcomes

The protocol defines a number of secondary endpoints in addition to the two key endpoints described in section 8.2 above. These analyses will be carried out for the final report. Selected secondary endpoints may also be analyzed for interim monitoring reports, to help evaluate the safety and efficacy of the investigational agent.

Below, the secondary outcomes from section 4.2.2 of the protocol are cited, with a short description of the analysis methods. For each outcome, the treatment group comparisons will be stratified by disease severity at study entry and by site pharmacy, as described in section 3 under “stratification”.

- Time to discharge for the initial hospitalization. Treatment groups will be compared using time-to-event methods that take into account the competing risk of death, similar to the analyses for time to sustained recovery described in section 8.1.
  - Hospital readmissions will be summarized using methods for recurrent events (i.e. those who are readmitted will re-enter the risk set).
- Days alive outside of a short-term acute care hospital up to day 90. For this analysis, the “last-off” method will be used, i.e., days from the latest hospital discharge to day 90 will be counted. A person who dies within 90 days will be assigned a value of 0, consistent with the approach taken in trials of intensive care-based interventions. We will present

the median days by group and test the hypothesis of no difference between arms with a Wilcoxon rank sum test.

- For interim analyses, only participants who have reached Day 90 (administrative follow-up for those who died) will be included, to avoid bias. Alternatively, a shorter time period may be used.
- Pulmonary+ and pulmonary ordinal outcomes on Days 1-7, and the pulmonary ordinal outcome on Days 14 and 28. The proportion of participants in each category of the pulmonary and pulmonary+ outcomes will be summarized over time (both outcomes at days 1-7, the pulmonary outcome also at Days 14 and 28); at each of those days, treatment groups will be compared using proportional odds models as described in section 3; the proportional odds models will be adjusted for the categories of the pulmonary+ outcome at baseline and for study site pharmacy. If participants in both disease severity strata are enrolled, the models will also be adjusted for the interaction between disease severity stratum and pharmacy.

Additionally, the ordinal outcomes will be dichotomized (“category 1”, “best 2 categories” through “best 5 categories”), and proportions will be compared between treatment groups at selected time points using logistic regression. For these analyses, the key dichotomized outcome considers the “best 2 categories”, which is similar to the “recovery” outcome in the ACTT-1 trial.

- *Clinical organ failure or serious infections*, defined by development of any one or more of the clinical events listed in [Appendix B](#), through Days 28 and 90. The development of *organ failure or serious infections* will be analyzed as a binary outcome, and the proportions of participants who developed *organ failure, serious infections or death* will be compared across arms using stratified CMH tests, overall and for individual components.
- A composite of death, clinical organ failure, or serious infection through Days 28 and 90 (see [Appendix B](#)). Treatment groups will be compared using standard time-to-event methods, since death is part of the outcome and not a competing risk. (Also described in section 7 as safety analysis).
- Outcomes assessed in other treatment trials of COVID-19 for hospitalized participants in order to facilitate cross-trial comparisons and overviews (e.g. 6-, 7-, and 8-category ordinal scales assessed at Days 1-7, 14 and 28; time to improvement in 1 or 2 categories of ordinal scale; time to best 3 categories of ordinal scale, and binary outcomes defined by improvement or worsening based on other ordinal outcomes). We will try to match the analyses in the other trials, to get results that can be compared. These analyses will not be performed for interim reports to the DSMB, unless requested.
- A composite of cardiovascular events (outcomes listed in items b1, e2 and e3 in [Appendix B](#)) and thromboembolic events (item f2). Time to event methods will be used that take into account the competing risk of death, e.g., Gray's test to compare treatment groups.

## 9 Subgroup Analyses

As stated in the protocol (section 11.2 in version 5.1), subgroup analyses for the primary efficacy outcome (time to sustained recovery) and for important safety outcomes will be performed. The goal is to determine whether and how the treatment effect (active versus control) differs qualitatively across various **subgroups defined at baseline**, and whether there are safety concerns in specific subgroups. Tests for heterogeneity of the treatment effect across subgroups will be carried out.

### 9.1 Outcomes, Subgroups, and Methods

The following outcomes will be considered for subgroup analyses:

- Time to sustained recovery (primary efficacy outcome)
- Time to the composite of *death, SAE, organ failure, or serious infections* through Day 90
- Time to death through Day 28, Day 90, and 18 months
- The composite of grade 3 and 4 events, SAEs, clinical organ failure, serious infections, or death through Day 5 and Day 28
- The Pulmonary and Pulmonary+ ordinal outcomes on Day 5
- Time to discharge from the index hospitalization, an outcome used in other COVID-19 trials.

To support the interpretation of the subgroup analyses for composite outcomes, components of the composites will also be analyzed.

Subgroup analyses will be performed by the following baseline factors:

- Disease severity (categories of the pulmonary+ outcome at study entry, randomization stratum). This subgroup analysis will be used at interim analyses after expansion of enrollment to assess if the treatment effect varies across the severity strata.
- Duration of symptoms prior to enrollment
- Age (18-49, 50-59, 60-69, 70-79, 80+)
- Biological sex
- Race/ethnicity
- Geographic location
- Level of residence (home) at the time COVID-19 symptoms developed
- Baseline pulmonary status (mutually exclusive subgroups: not on supplemental oxygen, supplemental oxygen < 4 L/min, supplemental oxygen  $\geq$  4 L/min, HFNC or NIV; invasive mechanical ventilation or ECMO)
- Body mass index (BMI)
- History of chronic conditions (cardiovascular disease, diabetes, asthma, chronic obstructive pulmonary disease, hypertension, chronic kidney disease, hepatic impairment, or cancer), and number of chronic conditions (none, 1, 2, 3 or more).
- Plasma antibody status. See section 9.2 below.
- Plasma antigen level. See section 9.2 below.
- SARS-CoV-2 viral RNA level based on midturbinate swab. See section 9.2 below.
- Biomarkers of inflammation and coagulation (including IL-6, hsCRP, and D-dimer)
- Concomitant medications, including subgroups formed by:

- Use of remdesivir prior to study entry (unless contraindicated, participants in both treatment groups were to receive remdesivir up to 10 days as background therapy)
- Use of corticosteroids (4 subgroup categories, formed by the combinations of supplemental oxygen use [yes/no] and corticosteroid use at study entry)

Subgroup analyses for the **composite safety endpoint at Day 5** will use logistic regression, stratified by disease severity at study entry. Within each subgroup, the number and percent of participants with events will be calculated by treatment group, and ORs with 95% CIs comparing the investigational agent versus control will be estimated. Global tests for heterogeneity of the treatment effect across subgroups will be carried out, by testing for interactions between the treatment group and the subgroup variable in an expanded model, as described above. Additionally, subgroup analyses for the composite safety endpoint **through Day 5** will be conducted using Cox proportional hazards models, stratified by disease severity.

Subgroup analyses for **all-cause mortality** and **safety endpoints** that are analyzed using time-to-event methods (through Day 5, Day 28 and through Day 90) will use stratified Cox proportional hazards models, since death is part of the composite endpoints and not a competing risk. HRs will be estimated with 95% CIs for each subgroup, and global tests of heterogeneity of the treatment effect will be carried out, as described above. The proportional hazards models will be stratified by disease severity.

Subgroup analyses for the **pulmonary** and pulmonary+ ordinal outcomes on Day 5 will use proportional odds models, adjusted for the pulmonary or pulmonary+ category at study entry. In order to summarize the distributions across the categories of the ordinal outcome, the mean score (using 1-7 for best to worst) will be calculated by treatment group within each subgroup. For each subgroup, summary ORs with 95% CIs will be calculated. Global tests for heterogeneity of the treatment effect across subgroups will be carried out, as described above.

Subgroup analyses for **time to discharge from the index hospitalization** will use the Fine-Gray model (with death as competing risk), stratified by disease severity at study entry. Similar analyses as described above for time to sustained recovery will be carried out.

Additionally, subgroup analyses will be conducted for subgroups formed by a disease progression risk score at baseline. The construction of this risk score has been published and will be revisited as data on the sustained recovery endpoint accumulate for new investigational agents.

Unless specified otherwise (e.g., the subgroups by nAb status at study entry for AZD7442 described in [Appendix E](#)), subgroup analyses will not be adjusted for multiple comparisons. Subgroup analyses will be interpreted with caution due to limited power and uncontrolled type I error.

